D.	Stı	udy Implementation							
	i.	Study Design	6						
	ii.	Study Procedure	7						
	iii.	Consent Procedure	7						
	iv.	Drug Administration	7						
	v.	Observations	8						
	vi.	Dose Modifications	9						
	vii.	Concurrent Treatment	9						
	viii	. Removal of Patients from Study	10						
Е.	Da	ta Collection							
	i.	Clinical Data	10						
	ii.	Adverse Events	10						
F.	Sta	atistical Considerations							
	i.	Overview	10						
	ii.	Sample-Size Calculations	11						
G.	Etł	hical Issues							
	i.	Informed Consent	11						
	ii.	Children as Research Subjects	11						
Н.	Ph	armaceutical Information							
	i.	Formulation	11						

N-Acetv	Icvsteine in BA	
11,1001	ii. Storage	11
	iii. Administration	12
	iv. Toxicities	12
I.	References	13
J.	Appendix	
	i. Data and Safety Monitoring Plan	17
	ii. Data and Safety Monitoring Board Charter	23

N-Acetylcysteine in BA **A. Objectives**

- 1) To determine if N-acetylcysteine (NAC) therapy normalizes total serum bile acids (TSBAs) within 24 weeks after Kasai portoenterostomy (KP) for biliary atresia (BA) (primary outcome)
- 2) To describe changes in laboratory markers for disease progression in the first two years of life (secondary outcome)
- 3) To describe changes in weight in the first two years of life (secondary outcome)
- 4) To describe occurrence of sentinel events related to worsening liver disease (cholangitis, development of ascites, variceal bleed, liver transplant listing, liver transplant, death) in the first two years of life (secondary outcome)
- 5) To document adverse events which may be associated with NAC therapy (secondary outcome)

B. Background and Rationale

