NAC has a number of properties that make it an especially attractive potential therapeutic agent. First, glutathione creates an osmotic gradient in the bile duct lumen which drives one-third of total bile flow in humans (the other drivers are bile acids and secretin/bicarbonate).^{7–9,14} Second, NAC is a Food and Drug Administration-approved therapy for another serious liver condition in neonates and children (acetaminophen overdose).¹⁵ It has also been used for other liver and non-liver indications in

Table: Other Studies Using IntravenousNAC in Neonates

Liver-related

- Parenteral nutrition associated cholestasis^{16,17}
- Nonacetaminophen acute liver failure^{18,19}
- Neonatal hemochromatosis (gestational alloimmune liver disease)²⁰
- Liver-unrelated
- Bronchopulmonary dysplasia²¹
- Chorioamnionitis^{22,23}

neonates, with few reported adverse events (Table).^{16–23} Third, glutathione is an anti-oxidant, which could

scavenge the free radicals contributing to cirrhosis. Fourth, glutathione is catalyzed into glycine, glutamate, and cysteine by gamma-glutamyl transferase (**GGT**), thereby potentially fulfilling a nutritive role for cholangiocytes.^{14,24,25} Preclinical studies are also promising, with glutathione's strong choleretic properties best established in rat flow studies and NAC's hepatoprotective effects documented in rescuing different mouse models of cholestasis.^{14,26–28}

To test our hypotheses, we will administer intravenous NAC continuously for seven days and determine the number of subjects with normal TSBAs (0-10 umol/L) within 24 weeks of KP. In addition, markers of BA progression, such as abnormal laboratory results, failure-to-thrive, and occurrence of complications related to chronic liver disease, will be described over the first two years of life. Finally, all adverse events occurring during NAC infusion and in the 21 days after its completion will be recorded. Our study employs the two-stage "minimax" Phase 2 clinical trial design, a design commonly used in oncological trials to determine whether a particularly therapy has sufficient activity to warrant a larger Phase 3 trial.²⁹ The two-stage "minimax" design offers two distinct advantages compared to other designs: (i) early termination if the drug is not efficacious; and (ii) small sample sizes, because historical controls rather than a separate control arm are used.

C. Enrollment Procedures

- i. Inclusion Criteria (all must be met)

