- Sentinel events during the study period related to liver disease, such as cholangitis, ascites, liver transplant listing, liver transplant, and/or death (see Data and Safety Monitoring Plan (DSMP) in Appendix)
- Adverse events in the first 28 days after KP possibly related to NAC, including rash, urticaria, pruritus, tachycardia, hypotension, vomiting, edema, anaphylaxis, and intravenous line issues (see DSMP in Appendix)
- **vi. Dose Modifications** Rules for modifying NAC infusion are as follows, based in part on prior recommendations for NAC therapy in acetaminophen toxicity (also see DSMP in Appendix):³⁵
 - a) Flushing alone, without pruritus, urticaria, or other serious signs
 - No intervention
 - Continue infusion, unless more severe signs develop
 - b) Urticaria
 - Stop infusion
 - Treat immediately with intravenous diphenhydramine (1.25 mg/kg/dose)
 - Restart infusion if symptoms resolve within 1 hour
 - c) Angioedema, hypotension, wheezing
 - Stop infusion
 - Treat with intramuscular epinephrine (0.01 mg/kg/dose), intravenous diphenhydramine (1.25 mg/kg/dose), intravenous glucocorticoid (1 mg/kg/dose), and/or inhaled albuterol, at the discretion of the clinical team
 - Do not restart infusion
 - Continue to follow patients for first two years of life, per study protocol
 - d) Elevation of ALT >700 U/L above baseline, Bc 3x above baseline, TB 3x above baseline, and/or Bc >5 mg/dL above baseline
 - Stop infusion
 - Do not restart infusion
 - Follow patients clinically until elevated ALT/Bc stabilizes/resolves
 - Evaluate for drug-induced liver injury if deemed appropriate by the clinical team, based on FDA recommendations (https://www.fda.gov/downloads/Drugs/.../guidances/UCM174090.pdf)
 - e) If a severe adverse event related to or possibly related to the study drug (see DSMP in Appendix for definition) occurs during the first 7 days of the trial, i.e., during NAC infusion, the infusion will be paused, and an emergency Data Safety Monitoring Board (DSMB) meeting will be convened. If the DSMB deems that causality is unrelated to NAC use, then the trial can be continued.

vii. Concurrent Treatments

a) Standard therapies: All standard therapies will be given during the study period, including ursodeoxycholic acid (20 mg/kg/day), fat-soluble vitamins (AquADEK, 1 ml once or twice daily), and up to one year of post-KP antibiotics (trimethoprim/sulfamethoxazole 5 mg/kg/day). In infants found

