to have low Vitamin A levels (<20 mcg/dL), intramuscular Vitamin A injections of 50,000 IU will be given two days before KP and 28 days after KP. Steroids will not be used as standard post-KP care.

b) Experimental therapies: No other investigational therapies will be given during the study period.

viii. Removal of Patients from Study

- a) Parents may voluntarily exclude their infant from the study at any time
- b) The investigators may remove a patient if the study team decides that continuation is not in the best interest of the participant of the study (i.e., patient receives another experimental therapy during the two-year study period that will confound the results).

E. Data Collection

- i. Clinical Data All clinical data (laboratory results, weights, occurrence of sentinel events) will be stored in the patient's electronic medical record. In addition, a comprehensive study form containing all data for each subject will be updated as new results become available.
- ii. Adverse Events All adverse events (observed by the study team, reported by parents, and/or detected by laboratory findings) will be recorded in the patient's medical record as well as separate form specifically for the study. The form will be submitted to the DSMB following a pre-determined schedule (see DSMP in Appendix).

F. Statistical Considerations

i. Overview

This is a Phase 2 clinical trial using the two-stage "minimax" design described by Simon.²⁹ As a Phase 2 trial, the trial's objective is to determine whether NAC

has sufficient biological activity as adjunctive therapy for BA to warrant further study. By choosing the two-stage "minimax" design, we gain two advantages: (i) early termination if the drug is not efficacious, and (ii) using historical controls and therefore an overall smaller sample size to test the hypothesis, i.e., no randomization or control arm. This study design only identifies large effects (response >20%). For BA this is appropriate, because the field is in need of a robust therapy that can substantially limit liver damage and delay/prevent need for liver transplantation.

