 - Help arrange logistics of DSMB meetings
 - Help prepare materials for DSMB meetings, including minutes of previous meeting, updated AE CRFs, and updated Data CRFs
 - Attend DSMB meetings
- c) Data Safety Monitoring Board
 - Convene via conference call before trial starts, to review protocol and decide on any amendments
 - Meet twice yearly via conference call to review trial progress, examine AE CRFs, examine Data CRFs, determine whether changes in the study are warranted, and determine whether the study should continue
 - Meet on emergency basis as determined by Chairperson
 - (Chairperson) Respond with recommendations within seven days to serious AEs reported by the Principal Investigator

• Adverse Events:

AEs as specified below occurring in the first 28 days after KP will be documented. An AE is defined as any unfavorable and unintended sign, symptom, laboratory finding, or disease temporally associated with the study, whether or not the AE is related to NAC therapy. These include events observed by the study team, reported by parents, and/or detected by laboratory findings. The following targeted AEs are reportable events in this study:

- a) Clinical AEs that are caused by NAC or likely caused by NAC (typically related to hypersensitivity and occurring at start of infusion):
 - Acute flushing
 - Skin erythema
 - Other rash
 - Urticaria

- Hypotension
- Tachycardia
- Edema
- Vomiting
- Wheezing
- Shortness-of-breath
- Bronchospasm
- Anapyhlaxis
- Redness/swelling/pain/bruising at intravenous line site
- Fluid infiltration at intravenous line site
- Vessel thrombosis at intravenous line site
- Infection at intravenous line site
- Loss of intravenous line
- b) Clinical AEs which could occur with BA in the first 28 days after KP, independent of therapy:
 - Increase in AST, ALT, and/or GGT >400 U/L above baseline (pre-KP) values (Note: in BA, baseline liver enzymes are already National Cancer Institute-Common Terminology Criteria for Adverse Events (CTCAE) Grade 3)
 - Increase in Bc >3 mg/dL above baseline (pre-KP) values (Note: in BA, baseline liver enzymes are already National Cancer Institute CTCAE Grade 3)
 - Increase in TB >5 mg/dL above baseline (pre-KP) values (Note: in BA, baseline liver enzymes are already National Cancer Institute **CTCAE** Grade 3)
 - Vomiting with feeds, requiring acid reduction therapy
 - Cholangitis, requiring antibiotic therapy
 - Infection of other etiology requiring treatment
 - Ascites
 - Diarrhea

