 - Complications related to surgery
 - Death

• Serious AEs

Serious AEs, which are a subset of AEs as specified below, occurring at any time during the study period will be documented. In addition, serious AEs will be reported to the DSMB Chairperson within seven days of occurrence with the exception of events related to the management of the natural course of BA (i.e., hospitalizations for cholangitis, poor growth, worsening liver disease after failed KP, etc). After reporting a serious AE, the Principal Investigator and/or study team will receive recommendations about how to proceed with the study within seven days. Serious AEs are those AEs which:

- a) Result in death;
- b) Place the subject at immediate risk of death (does not include AEs which, if more severe, might have caused death);
- c) Require inpatient hospitalization or prolongation of existing hospitalization (with the exception of hospitalizations related to the natural course of BA, such as hospitalizations for cholangitis, poor growth, worsening liver disease after failed KP, etc)
- d) Lead to persistent disability which prevents a subject from conducting normal life functions; or
- e) In the first 28 days after KP, elevation of ALT >700 U/L above baseline, Bc 3x or >5 mg/dL above baseline, and/or TB 3x above baseline.
- Dose Modifications for AEs (including serious AEs) related to NAC infusion (based in part on a previously published protocol)³⁵

- a) Flushing alone, without pruritus, urticaria, or other serious signs
 - No intervention
 - Continue infusion, unless more severe signs develop
- b) Urticaria
 - \circ Stop infusion
 - Treat immediately with intravenous diphenhydramine (1.25 mg/kg/dose)
 - Restart infusion if symptoms resolve within 1 hour
- c) Angioedema, hypotension, wheezing (serious AE)
 - Stop infusion
 - Treat with intramuscular epinephrine (0.01 mg/kg/dose), diphenhydramine (1.25 mg/kg/dose), intravenous glucocorticoid (1 mg/kg/dose), and/or inhaled albuterol, at the discretion of the intensive care unit team
 - Do not restart infusion
 - Continue to follow patients for first two years of life, per study protocol
- d) Elevation of ALT >700 U/L above baseline, Bc 3x or Bc >5 mg/dL above baseline, and/or TB 3x above baseline (serious AE)
 - Stop infusion
 - Do not restart infusion
 - Follow patients clinically until elevated ALT/Bc stabilizes/resolves
 - Evaluate for drug-induced liver injury if deemed appropriate by the clinical team, based on FDA recommendations

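### The adverse-event outcome is limited to events possibly related to NAC, so liver-test rises that meet the plan's own stopping criteria can drop out of it

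*Combined protocol and SAP*

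**What the plan says.** The operative outcome is in section D.v, secondary outcomes: "Adverse events in the first 28 days after KP possibly related to NAC, including rash, urticaria", followed by further clinical signs, intravenous line issues and a pointer to the DSMP. No liver event is among the examples. Objective 5 in section A is limited in the same way, to events with a possible link to NAC.

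Other places are wider. The opening summary names adverse-event reporting as a secondary objective and sets no relatedness condition. Section B says that "all adverse events occurring during NAC infusion and in the 21 days after its completion will be recorded". Section E.ii says: "All adverse events (observed by the study team, reported by parents, and/or detected by laboratory findings) will be recorded". The DSMP's definition of an adverse event (AE) applies regardless of relationship to NAC.

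The DSMP sorts its reportable events into two lists. List (a) holds events caused or likely caused by NAC and has no liver-test item. List (b), headed "Clinical AEs which could occur with BA in the first 28 days after KP, independent of therapy", holds the AST/ALT/GGT, conjugated bilirubin (Bc) and total bilirubin (TB) rises. Larger ALT, Bc and TB rises reappear under the DSMP heading "Dose Modifications for AEs (including serious AEs) related to NAC infusion", where they stop the infusion. Both there and in section D.vi(d) the follow-up includes: "Evaluate for drug-induced liver injury if deemed appropriate by the clinical team".

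**The concern.** A safety outcome filtered on judged causality is only as sound as the judgement. Here the team that gave the drug makes it, with no blinding and no control arm, in a disease that itself raises the same laboratory tests. If events put down to BA are left out, the reported result leans towards good tolerability. It could also omit the liver signal that the plan treats as serious enough to end the infusion. With at most 16 infants, one omitted case changes the summary.

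**Working it through.** **Step 1. The statements of scope side by side.**

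| Place | Relatedness condition |
|---|---|
| Opening summary | none (reporting) |
| Section A, objective 5 | possible link to NAC |
| Section B | none (recording) |
| Section D.v, AE outcome | possibly related to NAC |
| Section E.ii | none (recording) |
| DSMP, definition of an AE | none |
| DSMP, Serious AEs, item (e) | none |

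Recording is unfiltered. The two places that define the analysed outcome are filtered, and the summary disagrees with them.

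**Step 2. What the filter does to a liver-test rise.** The DSMP rating scale has four levels. Related needs clear evidence of a link to the drug. Possible needs two things: that BA, other therapies and other causes cannot explain the event, and that the timing is plausible. Unlikely/Remote applies when another explanation is more likely or the timing does not fit. Not related applies when BA or another cause readily explains the event. The DSMP itself notes that liver enzymes in BA are already CTCAE Grade 3 at baseline. A further rise after KP therefore fails the first condition for Possible whenever BA is accepted as an explanation.

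**Step 3. Whether the two DSMP headings cover the same events.**

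| Test | List (b), rise above baseline | Serious AE item (e) and stopping rule |
|---|---|---|
| ALT | >400 U/L | >700 U/L above baseline |
| AST, GGT | >400 U/L | none |
| Bc | >3 mg/dL | 3x, or >5 mg/dL above baseline |
| TB | >5 mg/dL | 3x above baseline |

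An ALT rise above 700 U/L is necessarily above 400 U/L, and a Bc rise above 5 mg/dL is necessarily above 3 mg/dL. Those events sit under both headings. For the 3x criteria the overlap depends on the baseline value. AST and GGT have no stopping criterion. The overlap is real but partial.

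**Step 4. Size.** The plan gives no expected rate of liver events, so the counts here are assumed. Exact (Clopper-Pearson) limits for k of n infants are: lower = 2.5% quantile of Beta(k, n−k+1); upper = 97.5% quantile of Beta(k+1, n−k). For k = 0 the upper limit is 1 − 0.025^(1/n). With n = 16 this is 1 − 0.794 = 0.206. With n = 12 it is 0.265.

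| Infants meeting the liver criteria, all rated Not related | Unfiltered outcome (95% CI) | Filtered outcome (95% CI) |
|---|---|---|
| 1 of 16 | 6.3% (0.2–30.2%) | 0/16 (0–20.6%) |
| 2 of 16 | 12.5% (1.6–38.3%) | 0/16 (0–20.6%) |
| 3 of 16 | 18.8% (4.0–45.7%) | 0/16 (0–20.6%) |

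**Step 5. Effect on the design.** The plan's only design figures are those of the two-stage rule in section F.ii. Rejection probability = sum over x = 1 to 12 of P(Bin(12,p) = x) × P(Bin(4,p) ≥ 3−x). This gives 0.0427 at p = 0.05 and 0.801 at p = 0.25, consistent with the stated 5% limit and 80% power. The AE definition does not enter this calculation.

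**The case against.** The strongest reply is that nothing is lost. The summary promises reporting without a relatedness condition. The D.v bullet uses an open-ended list and points to the DSMP, whose AE definition ignores relationship and makes both lists reportable. A rise meeting the stopping criteria is a serious AE with no relatedness condition, and all AEs to day 28 go to the DSMB at each meeting. AST/ALT, GGT, Bc and TB trajectories are separate secondary outcomes. All of this stands, with two qualifications. The expedited-report exception for the natural course of BA, which names worsening liver disease after failed KP, could leave some liver rises to the scheduled meetings. And a trajectory does not count the infants who crossed a threshold.

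Three stronger readings are tempting and are not supported:

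- A reader might infer that list (b) rules in advance that liver-test rises are unrelated to NAC. Its heading says only that such events can arise without the drug, and each event gets its own rating on the AE form.
- A reader might infer that liver injury would escape safety monitoring. The serious-AE and DSMB provisions say otherwise.
- A reader might size the problem by the share of reportable items in list (b). Death, cholangitis and ascites are also sentinel outcomes with no NAC filter, so that share overstates what could go unreported.

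It is also fair that a stopping threshold is a precaution and not a finding of cause. That softens the conflict between headings, but the DSMP still places the rule under events related to the infusion.

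**Conclusion.** The point holds as an inconsistency in the outcome definition with a foreseeable direction of bias. The wider statements show that the plan disagrees with itself. They do not cure the problem, because the operative outcome in D.v and objective 5 remain filtered, and the rating scale makes Possible hard to reach for a liver-test rise in BA. The conclusion assumes that the phrase in D.v is applied through the DSMP rating scale, which D.v points to but does not expressly adopt. The effect is confined to the reported AE outcome; collection, DSMB review and the primary analysis are untouched. The 0/16 versus 2/16 contrast illustrates how sensitive a trial of this size is to one or two attributions. It is not a prediction.

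**What to change.** - In D.v and objective 5, define the outcome as all AEs and serious AEs in the first 28 days after KP, regardless of judged relationship to NAC. Show the relationship rating as a column in the table and not as a condition for entry.
- Add one line to the outcome: the number and proportion of infants meeting the existing liver criteria in DSMP serious AE item (e), with an exact 95% CI. No threshold changes.
- Reconcile the opening summary, objective 5, D.v and the DSMP headings for list (b) and for dose modifications, so that one statement of scope applies and no heading appears to settle causality before an event is rated.

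The cost is wording only, since the events, ratings and laboratory values are already collected. The downside is a longer AE table that includes events of the underlying disease. Without a control arm, that table still cannot separate NAC effects from BA.

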 - a) Age less than or equal to 90 days at time of KP (standard age range in which KPs are performed)
 - b) BA diagnosis made by intraoperative cholangiography and KP performed at Texas Children's Hospital, Texas Medical Center Campus
 - c) Legal guardian(s) sign consent after understanding risks and investigational nature of study

ii. Exclusion Criteria

- a) Decompensated liver disease (INR >1.3) despite parenteral Vitamin K administration
- b) KP not performed for any reason (i.e., normal intraoperative cholangiography, or liver found to be too diseased intraoperatively to proceed with KP)
- c) Active respiratory infection
- d) Renal impairment, as defined by having an eGFR < 60 mL/min/1.73m² or creatinine clearance < 60 mL/min (https://www.niddk.nih.gov/health-information/communication-programs/nkdep/laboratoryevaluation/glomerular-filtration-rate-calculators/children-conventional-units)
- e) Presence of severe concurrent illnesses, such as pulmonary (i.e., bronchopulmonary dysplasia), neurological, cardiovascular, metabolic, endocrine, and renal disorders, which may be congenital or acquired, that would interfere with the conduct and results of the study
- **iii.** Total Planned Enrollment 12 subjects (minimum), 16 subjects (maximum); see below for discussion of sample size.
- iv. Inclusion of Women Male and female infants will be enrolled in this study. There may be more females than males enrolled, given that BA is slightly more common in females.
- v. Inclusion of Minorities Enrollment will be open to infants of all racial and ethnic backgrounds. Minority representation will reflect the racial/ethnic diversity of patients seen at the study hospital.
- vi. Inclusion of Children This trial will only enroll infants ≤90 days old.

D. Study Implementation

i. Study Design – This is an open label, Phase 2 study of seven days of intravenous NAC treatment after KP. Subjects will be followed for the first two years of life, and no additional clinic visits or testing beyond those routinely performed for routine BA clinical care at Texas Children's Hospital will be performed.

ii. Study Procedure

- a) Before KP
 - (1) Identify cholestatic infants likely to have BA who fulfill inclusion criteria
 - (2) Approach parent(s)/guardian(s) and explain study
- b) After KP until hospital discharge (typical length-of-stay 10-14 days)
 - (1) Consent parent(s)/guardian(s) and answer any remaining questions

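### Section D.viii(b) lets investigators remove an infant from two-year follow-up for receiving another experimental therapy, which can selectively thin the descriptive outcomes

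*Combined protocol and SAP*

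**What the plan says.** Under Removal of Patients from Study, section D.viii(b) provides that "The investigators may remove a patient if the study team decides that continuation is not in the best interest" of the participant. The single illustration is that the "patient receives another experimental therapy during the two-year study period that will confound the results". Directly before it, section D.vii(b) states: "No other investigational therapies will be given during the study period".

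The study depends on data from the whole of that period. Section D.i says: "Subjects will be followed for the first two years of life", using only visits and tests that belong to routine care. Objective 4 is "To describe occurrence of sentinel events related to worsening liver disease" over the first two years of life, and Objectives 2 and 3 cover laboratory markers and weight over the same time. The Data and Safety Monitoring Plan adds: "Serious AEs, which are a subset of AEs as specified below, occurring at any time during the study period will be documented".

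Where the infusion is stopped for angioedema, hypotension or wheezing, section D.vi(c) says: "Continue to follow patients for first two years of life, per study protocol". The protocol has no matching sentence for an infant removed under D.viii(b). It does not say whether data collection goes on after removal, or in which denominator the infant counts.

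**The concern.** NAC is given for seven days, and everything after that is observation. Taking an infant out of the study at, say, ten months stops no study treatment and spares no study procedure. Its only practical effect is to stop recording what happens next.

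The reason given for removal is confounding, and the people deciding know both the treatment and the infant's course. If a poor course makes another experimental therapy more likely, the infants lost would tend to be those heading for ascites, listing, transplant or death. Section F.i compares the secondary outcomes with published and institutional results, including published two-year outcomes for all infants receiving KP. A cohort that has shed some of its poor courses is not like for like with that comparator. With no control arm and at most 16 infants, one or two such losses would show.

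**Working it through.** **The plan's own figure.** No figure is stated for the two-year outcomes. The only stated operating characteristics belong to the primary outcome (section F.ii: stop at 0 of 12, reject at 3 or more of 16, null rate 5%, alternative 25%). With X ~ Bin(12, p) in stage one and Y ~ Bin(4, p) in stage two,

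P(reject) = P(X=1)·P(Y≥2) + P(X=2)·P(Y≥1) + P(X≥3).

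- p = 0.05: 0.3413 × 0.0140 + 0.0988 × 0.1855 + 0.0196 = 0.0427
- p = 0.25: 0.1267 × 0.2617 + 0.2323 × 0.6836 + 0.6093 = 0.8013

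These agree with the stated 5% and 80%. The rule uses only TSBA within 24 weeks of KP, so loss of later data does not enter it.

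**What removal does after day 7.** Three provisions are read together:

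- Study drug ends at about 168 hours (section D.iv(b)).
- Follow-up uses routine care only (section D.i).
- Removal is from the study, not from treatment (heading of section D.viii).

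After the infusion, removal can therefore end only data collection.

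**Size, event-free course (assumed counts).** The documents give no expected event rate and no expected number of removals. Assume 8 of 16 infants would be free of sentinel events, and that removed infants come from the other 8 and are dropped entirely:

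- none removed: 8/16 = 50.0%
- 1 removed: 8/15 = 53.3%
- 2 removed: 8/14 = 57.1%
- 3 removed: 8/13 = 61.5%

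**Size, event rate (assumed counts).** One infant is removed before an event that would have occurred:

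| Assumed true events | All kept | Dropped from denominator | Counted as event-free |
|---|---|---|---|
| 4 of 16 | 25.0% | 3/15 = 20.0% | 3/16 = 18.8% |
| 6 of 16 | 37.5% | 5/15 = 33.3% | 5/16 = 31.3% |
| 8 of 16 | 50.0% | 7/15 = 46.7% | 7/16 = 43.8% |
| 10 of 16 | 62.5% | 9/15 = 60.0% | 9/16 = 56.3% |

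One such removal lowers the observed rate by 2.5 to 6.3 percentage points over this range. If the event came before removal and the data are kept, that event still counts and the shift is smaller. Counting a removed infant as event-free makes the shift larger than dropping the infant. The plan does not say which handling applies.

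**The case against.** The trigger is already a departure from protocol, because D.vii(b) rules out other investigational therapy. Removal is also optional and limited to therapy that would confound. This stands: the count may be zero. But D.viii(b) itself foresees the event, so the plan should say what happens to the data.

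A reader might infer that the removed infants are the ones doing badly. The documents do not say so. NAC itself starts within 24 hours of KP, before its result is known, so experimental therapy need not be reserved for failing infants. The link to outcome is plausible, but it is an inference.

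The illustration rests on an assumed count, and the exact 95% interval for 8/16 runs from about 25% to 75%, far wider than the shift. That is true. The interval describes chance, however, and does not allow for a one-directional loss.

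Nothing says data from before removal are discarded, and section E.i keeps a study form with each subject's data. Complete deletion is therefore the extreme case.

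The contrast with D.vi(c) has limits. D.vi(d), on laboratory elevations, has no two-year sentence, so D.vi(c) is a precedent and not a general rule.

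On safety, a reader might take Objective 5 as a two-year outcome. It concerns events that may be associated with NAC and sets no two-year period. The basis for longer surveillance is the serious-event provision and section D.ii(d). The serious-event definition also leaves out hospitalizations for the natural course of BA, so part of what a failing infant experiences would not be captured there in any case.

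**Conclusion.** The point holds as a limited one. D.viii(b) permits removal from the study for a reason that, after day 7, can only cost data, and no provision keeps the infant in follow-up or in a denominator. The possible effect is a favourable shift in descriptive secondary outcomes and shortened serious-event surveillance. On the assumed 8 of 16, the shift is 50% to 53–62% for one to three infants dropped entirely, and less if events before removal count. This assumes that removals happen at all and that they fall on infants with a poorer course; neither is documented.

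A reader might go further and conclude that the primary test is compromised. The documents do not support that from this clause: the two-year outcomes play no part in the 3-of-16 rule. Removal before week 24 could reach the primary outcome only through the separate discretionary replacement provision in F.ii, and nothing here relies on that. Nor do the documents give grounds for abolishing best-interest removal; the difficulty lies in the example.

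**What to change.** Replace the example in D.viii(b) with a statement along these lines:

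> Receipt of another experimental therapy is recorded as a protocol deviation with its start date and does not by itself end follow-up. Unless consent is withdrawn, routine-care data, sentinel events and serious AEs continue to be collected to age two from available records.

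In section F, add that:

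- all treated infants stay in the denominators for death, transplant listing, transplant and the other sentinel events;
- laboratory values and weights after the start date are flagged;
- a sensitivity analysis censors at that date.

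Leave D.vii(b), the general best-interest clause and the primary endpoint definition unchanged.

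The cost is about one paragraph in D.viii and a few lines in F, with no added visit or test. The downsides are the flag on later values and possibly incomplete records for an infant treated elsewhere, since follow-up rests on routine care at one hospital.
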